6.3.2 Treatment assignment, randomization

No randomization will be performed in this study. The assignment of treatment will depend on the previous study treatment assignment.

At Visit 201 (Week 0), all eligible subjects will be assigned to investigational treatment via Interactive Response Technology (IRT). All subjects will receive 120 mg s.c. q4w except subjects treated with 72 mg s.c. q4w in the core studies CQGE031C2302 or CQGE031C2303, who will continue to receive 72 mg s.c. q4w in this extension study for the first 12 weeks (see [Section 3.3](#) and [Section 6.1.3](#)). The investigator or his/her delegate will contact the IRT after confirming that the subject fulfills all the inclusion/exclusion criteria. The IRT will assign the subject, to a treatment arm and will specify a unique medication number for the package of investigational treatment to be dispensed to the subject. All kits of study treatment assigned by the IRT will be recorded in the IRT system.

The treatment assignment list for subjects will be reviewed and approved by a member of the Randomization Office.

6.4 Treatment blinding

[figure not shown]
Subjects, investigator staff and personnel performing the study assessments for studies CQGE031C2302 and CQGE031C2303 will remain blinded to the identity of the treatment from the time of enrollment (Visit 201, Week 0) until all subjects in this study have completed Week 12 in the first half of the treatment period and the primary analysis has been completed. An unblinded study monitor will visit the study site to monitor study drug related administration (see [Section 11.3](#)).

Should additional analysis be required to support Health Authority interactions (prior to the primary analysis), sponsor team members may be unblinded for such analysis. These unblinded team members will not be further involved in the study conduct until the primary analysis has been completed.

No blinding is required for subjects transitioning from study CQGE031C2202 and CQGE031C1301, as all subjects will receive 120 mg s.c. q4w ligelizumab.

Treatment blinding will be maintained at Visits 201, 202 and 203 (Weeks 0, 4 and 8) when subjects are being administered with liquid in vial (see [Section 3.3](#)) using the following methods:

1. Treatment assignment data are kept strictly confidential until the time of unblinding, and will not be accessible by anyone else involved in the study with the following exceptions:
 - Bioanalyst (█): to enable identification of samples from the ligelizumab treatment arms of the study to facilitate bioanalysis;
 - Independent personnel (external to Novartis) involved in monitoring anaphylaxis, neoplastic and cerebro-cardiovascular events (Adjudication Committee members), if needed; and
 - An independent DMC (see [Section 10.2.3](#)) and the independent statistician supporting the DMC activities ([Table 6-3](#)).
 - These personnel will not be involved in any other trial activities.

2. The following measures will be applied to keep the subject and study personnel blinded despite differences of the investigational treatments in volume:
- The investigational drug must be prepared by an independent unblinded pharmacist (or authorized delegate) and administered by an independent unblinded administrator who are both not involved in any of the study assessments. If an unblinded pharmacist is not available, preparation and administration of the investigational drug may also be performed by a single independent unblinded site person if he/she is authorized to do both.
 - Preparation of the investigational drug must be done in a separate space/room where subjects and blinded study personnel have no access during time of preparation.
 - To blind the liquid volume in the syringe, one method is to cover the syringe by a strip of opaque tape. The differences in length of the syringe plunger, related to the differences in the volume, should also be covered by the way of administration (see Pharmacist Manual).
 - The prepared syringes must be placed on a tray which is covered by an opaque towel to ensure the syringes are not visible to the subject at any time.
 - The independent unblinded authorized site persons (pharmacist/administrator) should not communicate the volume and any perceived sensation associated with the administration of the investigational drug.
 - The subject will be instructed to look away, from the tray of prepared syringes (whenever the tray is uncovered) and from the injection site.

The procedural details relating to treatment blinding and unblinded drug administration will be described in the Pharmacist Manual, which is provided separately.

Unblinding will occur in the case of subject emergencies.

Health authorities will be granted access to unblinded data if needed.

Table 6-3 Blinding and unblinding plan (applies to all subjects in this study transitioning from the core studies till completion of Week 12 in the first half of the treatment period and the primary analysis has been completed)

Role	Time or Event			DMC Analysis	Any additional analyses to support health authority interactions prior to primary analysis
	Treatment assignment list generated	Treatment allocation & dosing	Safety event (single subject unblinded)		
Subjects	B	B	B	B	B
Investigator and Site staff	B	B	UI	B	B

Role	Time or Event			DMC Analysis	Any additional analyses to support health authority interactions prior to primary analysis
	Treatment assignment list generated	Treatment allocation & dosing	Safety event (single subject unblinded)		
Unblinded site staff e.g., pharmacy staff and investigational drug administrator	B	UI	NA	B	B
Global Clinical Supply and Randomization Office	UI	UI	UI	UI	UI
Unblinded sponsor staff e.g., for study treatment re-supply, unblinded monitor(s)	B	UI	NA	B	B
Unblinded Pharmacovigilance sponsor staff	B	B	UI	B	B
Trial Statistician/statistical programmer	B	B	B	B	B
Independent Statistician/statistical programmer	B	B	B	UI	UI
Independent committees used for assessing interim results, if required (e.g., DMC)	B	UI	UI	UI	UI
Adjudication committee	B	B	B*	B	B
Bioanalyst ()	B	UI	B	B	B
All other sponsor staff not identified above (trial team, project team, management & decision boards, support functions)	B	B	B	B	B
Unblinded sponsor team for additional analyses (if needed)	B	B	B	B	UI

UI: Allowed to be unblinded on individual subject level

B: Remains blinded

NA: Not applicable to role

*Unblinded if needed

6.5 Dose escalation and dose modification

6.5.1 Dose modifications

Investigational drug dose adjustments are not permitted.

Any interruption of investigational drug administration should be discussed with Novartis or delegate regarding the subject's eligibility to continue investigational treatment.

Any missed or altered investigational drug administration must be recorded on the appropriate eCRF in order to reconstruct an accurate dosing history for each subject.

6.5.2 Follow-up for toxicities

Not applicable.

6.6 Additional treatment guidance

6.6.1 Treatment compliance

Subjects will have one s.c. injection every 4 weeks at 13 visits during the first half of the treatment period and for 48 weeks at 13 visits during the second half of the treatment period. For the first 3 treatment visits, the subjects will receive the injection as liquid in vial and thereafter as PFS.

The investigator must promote compliance by instructing the subject to take the study treatments (investigational, background and rescue medications) exactly as prescribed, by stating that compliance is necessary for the subject's safety and the validity of the study data. The subject must also be instructed to contact the investigator if he/she is unable, for any reason, to take the study treatment as prescribed.

For subjects receiving investigational treatment at the site, compliance is assured, as study drug must be administered by study personnel via s.c. injection.

For subjects self-administering investigational treatment, compliance will be assessed by the investigator and/or study personnel at each in-clinic visit (see [Table 8-1](#)) using medication package counts and information provided by the subject. This information should be captured in the source document and corresponding eCRF at each in-clinic visit. All study treatment dispensed and returned must be recorded as per [Section 6.7.1](#).

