6.1.4 Treatment duration

As described above in [Section 3](#) and [Section 4.2](#), the longest possible treatment is 104 weeks however this treatment might not be continuous and might span over a period of 156 weeks due to possibly entering the observation period.

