6.7 Preparation and dispensation

Each study site will be supplied with investigational study drug in kits as described under [Section 6.7.1.1](#).

Please refer to the Pharmacist Manual and Instructions For Use (IFU) for drug preparation and administration.

A unique medication number is printed on the study medication label.

Investigator staff will identify the study medication kits to dispense to the subject by contacting IRT and obtaining the medication number(s). The study medication has a 2-part label (base plus tear-off label). Immediately before dispensing the study medication kit to the subject, site personnel will detach the outer part of the label from the packaging and affix it to the source document.

From Visit 207 (Week 24), selected subjects will perform outside of clinic administrations at the protocol specified time points. For these cases, the investigator (or authorized delegate) will dispense, via IRT, an appropriate number of investigational treatment kits for outside of clinic administrations and detach the outer part of the label from the packaging in order to adhere it on the drug accountability log. Please refer to [Section 6.7.1](#) for returning and recording study treatment.

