Subjects who self-administered in the first half of treatment period and continuing straight into the second half of treatment (i.e. without transitioning into the second observation period) will continue to self-administer in the second half of treatment. These subjects do not have to be re-evaluated or re-trained at Week 64.

Visit 204 (Week 12) or Visit 403 (Week 64) – assisted

- The site staff will show the subject how to use the PFS based on the instructions provided in the IFU, with emphasis on specific checks for device use evaluation.
- The subject will be given the opportunity to raise questions if any
- The subject will perform the injection into an appropriate injection site of the body with the site staff **actively assisting** them during the injection. If the site staff observes that the subject is performing an action that may jeopardize the subject's safety, site staff will intervene to prevent any potential harm and guide/correct the subject.

Visit 205 (Week 16) or Visit 404 (Week 68) - assisted

- Study staff should ask the subject whether they wish to be retrained prior to injection. If needed, site staff will retrain the subject.
- The subject will perform the injection into the appropriate injection site of the body with the site staff **actively assisting** them during the injection.

Visit 206 (Week 20) or Visit 405 (Week 72) - supervised

- The subject will perform the injection into the appropriate injection site of the body mimicking an outside of clinic administration i.e. **without the active assistance** of the site staff but under their supervision.
- If the site staff observes that the subject is performing an action that may jeopardize the subject's safety, site staff will intervene to prevent any potential harm and guide/correct the subject.
- The site staff will observe that the dose is administered in accordance to the steps indicated in the self-injection assessment list and the potential hazard assessment list as described in the pharmacist manual. The site staff will observe the subject actions as per the lists to evaluate if the subject is capable of self-administration outside of clinic.

Thereafter, outside of clinic administrations should be done at pre-defined time points as per assessment schedule (Table 8-1). If self-administration is not chosen, these administrations can be performed by a trained caregiver who will then be trained as outlined above.

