Subjects carrying out self-administration **outside the clinic** setting will:

- have in-clinic safety and efficacy assessments done at 12 to 16 week intervals and will be provided with three/four kits for self-administration outside of the clinic; and
- be assessed remotely (i.e. outside of clinic) by safety phone call from the site every 4 weeks, unless there is an in-clinic visit scheduled (at 12 to 16 week intervals per protocol).

During outside of clinic administrations, subjects are expected to contact the investigator/site staff in case they are experiencing any AE/SAEs or have any concerns.

At any time during the study, should a self-administering subject, caregiver or investigator decide not to continue with self-administration, the subject must contact the site, or the site staff must contact the subject, to arrange for all subsequent visits and treatments to be administered at the site.

All study drug dosages prescribed and dispensed to the subject and all dosing errors or missed administrations during the study must be recorded on the appropriate eCRF.

All kits of study treatment assigned by the IRT will be recorded in the IRT system. The investigator must promote compliance by instructing the subject to take the study treatment

exactly as prescribed and by stating that compliance is necessary for the subject's safety and the validity of the study. The subject must also be instructed to contact the investigator if he/she is unable, for any reason, to take the study treatment as prescribed.

7 Informed consent procedures

Eligible subjects may only be included in the study after providing (witnessed, where required by law or regulation), IRB/IEC (Institutional Review Board/Independent Ethics Committee)-approved informed consent.

If applicable, in cases where the subject's representative(s) gives consent (if allowed according to local requirements), the subject must be informed about the study to the extent possible given his/her level of understanding. If the subject is capable of doing so, he/she must indicate agreement by personally signing and dating the written informed consent document.

Informed consent must be obtained before conducting any study-specific procedures (e.g. all of the procedures described in the protocol). The process of obtaining informed consent must be documented in the subject source documents.

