Days	-28 to -7	-14 to -1	1	29	57	85	113	141	169	197	225	253	281	309	337	365	393	421	449	477	505	533	561	589	617	645	673	701	729/ EOT	
Weeks	-4 to -1	-2 to -1	0	4	8	12	16	20	24	28	32	36	40	44	48	52	56	60	64	68	72	76	80	84	88	92	96	100	104	
Informed Consent	X ⁶																													
Inclusion / Exclusion criteria	X	X	X																											
Demography	X																													
Relevant medical history (including CSU history) ⁸	X																													
Prior urticaria treatment	X																													
Prior urticaria non-drug therapy	X																													
Family malignancy history ⁹	X																													
Prior and Concomitant medication usage	X	X	X	X	X	X	X	X	X	X	X	X	X	X	X	X	X	X	X	X	X	X	X	X	X	X	X	X	X	X
Surgery and procedures	X	X	X	X	X	X	X	X	X	X	X	X	X	X	X	X	X	X	X	X	X	X	X	X	X	X	X	X	X	X
Rescreening (rescreening eCRF should be recorded if the subject is rescreened)	X																													
Rescue medication usage	X	X	X	X	X	X	X	X	X	X	X	X	X	X	X	X	X	X	X	X	X	X	X	X	X	X	X	X	X	X
Dispense H1-AH rescue medication ¹⁰	S	S	S	S	S	S	S	S	S	S ¹¹	S ¹¹	S	S ¹¹	S ¹¹	S	S	S ¹¹	S ¹¹	S	S ¹¹	S ¹¹	S	S ¹¹	S ¹¹	S	S ¹¹	S ¹¹	S ¹¹	S	
Dispense oral corticosteroid rescue medication ¹²						S	S	S	S	S ¹¹	S ¹¹	S	S ¹¹	S ¹¹	S	S	S ¹¹	S ¹¹	S	S ¹¹	S ¹¹	S	S ¹¹	S ¹¹	S	S ¹¹	S ¹¹	S ¹¹	S	
Dispense Subjects' eDiary	S																													
Collect Subjects' eDiary																														
Visit at the site	X	X	X ¹⁴	X ¹⁴	X ¹⁴	X	X	X	X ¹⁵	X ¹³	X ¹³	X	X ¹³	X ¹³	X	X ¹⁴	X ¹⁴	X ¹⁴	X	X ¹³	X ¹³	X	X ¹³	X ¹³	X	X ¹³	X ¹³	X ¹³	X	

[figure not shown]
Epoch	Screening		-----First half of the Treatment----->																								-----Second half of the Treatment----->							
	Visit Numbers ¹	1 ²	2 ³	201	202	203	204	205	206	207	208	209	210	211	212	213	214 ^{4,5}	401	402	403	404	405	406	407	408	409	410	411	412	9998				
Days	-28 to -7	-14 to -1	1	29	57	85	113	141	169	197	225	253	281	309	337	365	393	421	449	477	505	533	561	589	617	645	673	701	729/EOT					
Weeks	-4 to -1	-2 to -1	0	4	8	12	16	20	24	28	32	36	40	44	48	52	56	60	64	68	72	76	80	84	88	92	96	100	104					
Safety phone call ¹⁵										X	X		X	X			X	X		X	X		X	X		X	X	X						
Contact IRT	X		X	X	X	X	X	X	X ¹⁶	X	X	X ¹⁶	X	X	X	X ¹⁶	X	X	X ¹⁶	X	X	X ¹⁶	X	X	X ¹⁶	X	X	X	X					
Liquid in vial investigational study drug administration			X	X	X																													
PFS investigational study drug administration						X	X	X	X	X	X	X	X	X	X	X ¹⁷	X	X	X	X	X	X	X	X	X	X	X	X	X					

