If discontinuation of investigational treatment occurs, the investigator should make a reasonable effort to understand the primary reason for the subject's premature discontinuation of investigational treatment and record this information. Always consider reasons which are related to safety and efficacy first.

Subjects who discontinue investigational treatment or who decide they do not wish to participate in the study further should NOT be considered withdrawn from the study UNLESS they withdraw their consent (see [Section 9.1.3](#)). They will be expected to perform the Visit 9998/EOT (Week 104) assessments 4 weeks after their last dose and will be expected to perform assessments at follow-up Visit 9999, 12 weeks after Visit 9998/EOT. If they fail to return for these assessments for unknown reasons, every effort (e.g., telephone, e-mail, letter) should be made to contact the subject/pre-designated contact as specified in [Section 9.1.4](#). This contact should preferably be done according to the study visit schedule.

For subjects who wish to prematurely discontinue treatment prior to the primary endpoint for any reason, every effort should be made to have them continue study visits as per the assessment schedule, at least until Visit 204 (Week 12). At the final visit, all dispensed investigational product should be reconciled and the AE and concomitant medications reconciled on the appropriate eCRF.

If the subject cannot or is unwilling to attend any visit(s), the site staff should maintain regular telephone contact with the subject, or with a person pre-designated by the subject. This telephone contact should preferably be done according to the study visit schedule until a decision is made to return to the site for discussion about ongoing treatment, or to discontinue treatment/study.

The investigator must also contact the IRT to register the subject's discontinuation from study treatment.

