12.3 Treatments

The Safety set will be used for the analyses below. Categorical data will be summarized as frequencies and percentages. For continuous data, mean, standard deviation, median, 25th and 75th percentiles, minimum, and maximum will be presented.

The number of subjects and the duration of exposure to investigational drug and dose will be summarized by treatment. Duration of exposure is defined as the date of the last treatment minus the date of first investigational drug administration plus 4 weeks (28 days).

In addition, the number of doses, total cumulative dose, and number of missed doses will be presented. A partial dose will be considered as if 100% of the dose of the assigned treatment has been administered.

Concomitant medications and significant non-drug therapies prior to and after the start of the study treatment will be listed and summarized according to the Anatomical Therapeutic Chemical (ATC) classification system. Concomitant medications will be summarized for the safety set separated for urticaria related background medications and non-urticaria related medications. Similarly, use of rescue medication will also be summarized.

[figure not shown]

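### As extracted, Table 8-1 marks a 14th second-half dose at Visit 9998 (Week 104/EOT), where Protocol 6.6.1 plans 13 ending at Week 100

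*Protocol*

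**What the plan says.** Section 6.6.1 of the protocol gives one injection every 4 weeks at 13 visits in the first half of treatment, and then injections "for 48 weeks at 13 visits during the second half of the treatment period".

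In Table 8-1, the row labelled "PFS investigational study drug administration" is marked, as extracted, at every visit from 204 to 214, at 401 to 412, and at 9998 (Week 104/EOT). The row for outside-of-clinic PFS administration also runs through 9998. None of the listed footnotes withdraws a dose at 9998.

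Other provisions that bear on the last dose:

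- Section 6.1.4: "the longest possible treatment is 104 weeks".
- Section 12.3: exposure is the last treatment date minus the first, plus 28 days.
- Section 9.1.1: subjects who discontinue treatment are to "perform the Visit 9998/EOT (Week 104) assessments 4 weeks after their last dose".
- Section 3.3 names the last first-half dose (Visit 213, Week 48). Section 3.5 names no last second-half dose.
- Section 6.1.3 gives the second-half range as Visits 214 to 9998/EOT, which does not say whether a dose is given at the end.
- SAP 2.3.4, in its rule for the end date of the second treatment half, lists visits 214 and 401 to 412 and leaves out 9998.

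**The concern.** The text and the schedule disagree by one dose. Table 8-1 is operative: section 6.7.2 says that "outside of clinic administrations should be done at pre-defined time points as per assessment schedule", citing this table. With no sentence in 3.5 or 6.1.3 that names the final dose, a site reading only the table would expect to dose at the end-of-treatment visit.

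At stake is one 120 mg injection that the protocol does not intend, given at the visit meant to close treatment. The spacing of follow-up would change with it. Visit 9999 is timed from Visit 9998, so a dose at 9998 shortens the interval between the last dose and the last safety visit for subjects on the 12-week follow-up.

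**Working it through.** **Step 1. Reproduce 6.6.1.** Dosing is every 4 weeks.

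- First half, Weeks 0 to 48: 48/4 + 1 = 13 doses (Visits 201 to 213).
- Second half, Weeks 52 to 100: (100 − 52)/4 + 1 = 13 doses (Visits 214, 401 to 412), spanning 100 − 52 = 48 weeks.
- Total: 13 + 13 = 26. The stated 13 visits and 48 weeks are reproduced, with the last dose at Week 100.

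**Step 2. Count Table 8-1.** The visit columns are 1, 2, 201 to 214, 401 to 412 and 9998, 29 in all.

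- Liquid-in-vial row: 3 marks (201 to 203).
- PFS administration row: 10 marks (204 to 213) + 1 (214, with footnote 17) + 12 (401 to 412) + 1 (9998) = 24. Section 6.6.1 implies 26 − 3 = 23.
- Second half: (104 − 52)/4 + 1 = 14 doses, spanning 52 weeks. Total: 3 + 24 = 27.

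**Step 3. Exposure on the uninterrupted schedule.** Table 8-1 puts Week 100 at Day 701 and Week 104 at Day 729. By the 12.3 rule:

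| Last dose | Exposure | Against the 104-week maximum |
|---|---|---|
| Visit 412, Day 701 | 701 − 1 + 28 = 728 days = 104 weeks | equal |
| Visit 9998, Day 729 | 729 − 1 + 28 = 756 days = 108 weeks | 4 weeks over |

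**Step 4. Take-home supply.** Footnote 16, which covers take-home kits, is last attached to the IRT row at Visit 409 (Week 88). Under 6.7.2 a subject "will be provided with three/four kits for self-administration outside of the clinic". Four kits at Week 88 cover Weeks 88, 92, 96 and 100 and no further. The safety phone-call row, which stands in for site visits during self-administration, ends at 412 and is blank at 9998.

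**Step 5. Follow-up interval.** Under section 3.6 the 12-week follow-up applies to subjects without 104 continuous weeks of treatment. Among those who reach Visit 9998 on schedule, these are the subjects who re-entered from the second observation period. Visit 9999 is 12 × 7 = 84 days after Visit 9998.

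- Last dose at Visit 412: 28 + 84 = 112 days to Visit 9999.
- Last dose at Visit 9998: 84 days to Visit 9999.
- Treatment-emergent window (12.5.2): 16 × 7 = 112 days.
- Adverse event monitoring (10.1.1) runs at least 30 days past the end-of-study visit: 84 + 30 = 114 days, which still covers 112.

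On the 52-week follow-up, Visit 9999 is at Day 1093, so 1093 − 729 = 364 days remain even after a Week 104 dose.

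**The case against.** The strongest objection is that this rests on one mark in a table read from PDF by a program. Some rows of the same table are visibly misaligned (vital signs and physical examination sit a column away from the laboratory rows). Footnote 31 has no anchor in the extracted table, so at least one superscript was lost. This stands as a reason to check the printed cell. It does not remove the point: the vial, self-administration training and phone-call rows fall where the text puts them, footnote 17 falls on Visit 214, and a column shift moves marks without adding one. Twenty-four marks do not fit 23 doses.

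A second objection is that the protocol already settles the schedule, because 6.6.1, 6.1.4 and 9.1.1 all point to Week 100. That is right, and it is why the mark is best read as stray. It does not make the table harmless, since the table is where sites look up the timing of doses.

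A third is that the harm is conditional. Section 6.7 has kits identified through IRT, and the IRT set-up at Visit 9998 is not in the documents. Table 8-1 does mark an IRT contact there, but that may only register completion. This also stands.

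Three stronger readings are tempting and are not supported:

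- A reader might infer that 84 days breaches the period of about 4 months, or 5 half-lives, in exclusion criterion 24. That criterion sets how long contraception continues after the last dose. Its clock moves with the dose, and it sets no deadline for Visit 9999.
- A reader might infer that a correctly dosed subject will be reported with one missed dose. SAP 2.4.1 presents missed doses but does not say that the expected number is taken from the marks in Table 8-1.
- A reader might infer that treatment-emergent events would be lost. Step 5 shows that monitoring still covers the window. Only the last scheduled visit and its laboratory tests come earlier relative to the dose.

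**Conclusion.** Wrong as written, and minor. As extracted, Table 8-1 schedules 14 second-half doses (27 in total, 108 weeks of exposure) against 13 (26 in total, 104 weeks) in the text. The text is the better evidence of intent: 6.6.1 states the count, 6.1.4 the maximum, and 9.1.1 the 4-week gap to EOT for those who discontinue. The SAP 2.3.4 visit list agrees, although it is a rule for a period's end date and not a dosing list.

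Followed literally, the table gives one unintended 120 mg dose at EOT. For subjects on the 12-week follow-up, Visit 9999 and its laboratory tests then fall 84 rather than 112 days after the last dose. The Week 12 primary endpoint is unaffected, as are subjects who stop early and those on the 52-week follow-up.

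This assumes that the printed table carries the mark, and any actual effect assumes that a kit was released at Visit 9998. The number of subjects affected is not given. The study was terminated early, section 9.1.5 handles subjects at termination as treatment discontinuers, and SAP 2.8.1.3 and 2.14.1 drop the continuous 104-week subpopulation from the final analysis. Few or no subjects may be affected.

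**What to change.** Check the Visit 9998 column in the printed Table 8-1. If the marks are there:

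- delete them from the PFS administration row and the outside-of-clinic PFS row;
- state in 3.5 or 6.1.3 that the last second-half dose is at Visit 412 (Week 100), as 3.3 does for Visit 213;
- in the study report, list any dose given at Visit 9998.

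The cost is two table cells, one sentence and one listing, which may turn out empty. No analysis changes.
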